7.2.2 Exploratory analyses

We will evaluate the acceptability of anal cancer screening based on survey responses regarding participant satisfaction at each study visit ([Appendix XIII](#) and [XV](#)) and phone call surveys ([Appendix XIV](#)) administered after study visits 1, 3,

and 5. Descriptive statistics will be used to characterize participants' acceptability of undergoing anal screening with cytology/HPV and HRA throughout the study to evaluate changes in perceptions. Generalized estimating equations (GEE) will be used to assess acceptability over time adjusting for intrapatient variability. Acceptability will be correlated with clinical and behavioral risk factors, e.g., history of sexual assault, depression, anxiety, medication compliance, sexual behaviors using GEE methods.

A fully de-identified dataset from the study, which will include data obtained on quality of life, anxiety, costs, and procedures, will be made available to [name], MD Anderson, for an economic evaluation of cost effectiveness modeling of anal cancer strategies in HIV-positive women.

8.0 DATA COLLECTION AND MONITORING

8.1 CRF Instructions

Access to the internet data entry system for this study, AdvantageEDCSM, and instructions for recording of study data on CRFs will be provided by the AMC ODMC at www.amcoperations.com. Participating institutions are responsible for submitting data and/or data forms via AdvantageEDCSM in accordance with the AMC Data Entry Guide and specific form instructions, within the timelines specified by the AMC's Standards of Procedure for Site Performance Measures.

8.2 Data Quality

It is the responsibility of the AMC ODMC to assure the quality of data for the study (See [Appendix VIII](#), AMC Data and Safety Monitoring Plan). This role extends from protocol development to generation of the final study database.

8.3 Data Monitoring

This study will be monitored in compliance with AMC policies and by the Clinical Data Update System (CDUS) Version 3.0. Cumulative protocol- and participant-specific CDUS data will be submitted electronically to CTEP on a quarterly basis. Reports are due January 31, April 30, July 31, and October 31. Instructions for submitting data using the CDUS can be found on the CTEP Web site (<http://ctep.cancer.gov/reporting/cdus.html>).

The AMC ODMC is responsible for compiling and submitting CDUS data to CTEP for all participants and for providing the data to the Principal Investigator for review.

8.4 Clinical Monitoring

The protocol chairs, AMC statistician, and AMC medical monitor will meet via conference call to review the protocol progress every 6 months until the final participant completes the last study evaluation. At all reviews, careful considerations should be given to the following items:

Prevalence and incidence of HSIL. The sample size calculation was done using a prevalence of 10%. Substantial differences in prevalence in this study may require recalculation of the sample size and length of follow-up.

Number of missing visits and number of early study discontinuations, and their effects on the length of intervals and loss to follow up.

Reported adverse events.

The protocol team members noted above will review these items and determine whether any modification to the study is required. If consensus about study modification or restarting the study is not reached among these members, then the issue will be referred to the AMC Executive Committee for a decision.

The protocol chairs will monitor the quality of HRA data on a per-site basis. Only the HRA results for the enrollment visit (V1) will be reviewed. Specifically, the protocol chairs will review the proportion of participants with HSIL at each site, stratified by cytology result (normal vs. abnormal). It is anticipated that the proportion of participants with HSIL to be at least 30% in those with abnormal cytology. The median number of biopsies performed

per participant at each site will also be reviewed.

Sites with performance evaluations that do not meet to the specified goals will be contacted by the protocol chairs for discussion and then brought to the attention of the HPV working group's HRA certification committee for re-evaluation.

9.0 ETHICAL AND REGULATORY CONSIDERATIONS

9.1 IRB Review and Informed Consent

The principles of IRB approval and informed consent described in the Department of Health and Human Services (DHHS) regulations for the Protection of Human Subjects (45 CFR Part 46) must be followed. IRB approval of the protocol and the informed consent form must be given in writing.

The sponsor's designee (AMC ODMC) must receive a copy of the letter of approval from the IRB, which specifically approves the protocol and informed consent, before participant enrollment. The IRB must also approve any significant changes to the protocol and documentation of this approval must be sent to the AMC ODMC. The IRB must review the research project at least once every 365 days during the duration of the project. Continuing approval of the project must also be given in writing and provided to the AMC ODMC.

Records of all study review and approval documents must be kept on file by the Investigator and are participant to inspection during or after completion of the study. AEs must be reported to the IRB according to local procedures. The IRB should receive notification of completion of the study and final report within 3 months of study completion and termination. The Investigator will maintain an accurate and complete record of all submissions made to the IRB, including a list of all reports and documents submitted.

Written informed consent will be obtained from the participant. The nature and significance of the risks associated with the study must be explained to the participant. The informed consent will describe the purpose of the study, the procedures to be followed, the risks and benefits of participation, all risks of the investigational agent(s) and/or study participation as listed in the model informed consent form, and all other elements of informed consent as required by regulation. A copy of the consent form will be given to the participant to keep.

In addition, any institution(s) conducting research according to the guidelines of this protocol is required to adhere to local and national laws and regulations governing the confidentiality and disclosure of health information.

9.2 Changes to the Protocol

Any change or addition to this protocol requires a written protocol amendment that must be approved by CTEP and the Investigator before implementation. All amendments require approval by the IRB of the treating institution. A copy of the IRB's written approval must be sent to the ODMC.

9.3 Women and Minorities

This study is being conducted by the NCI-sponsored AIDS Malignancy Clinical Trials Consortium (AMC). As part of their contractual obligations, each participating site within the AMC and the AMC as a whole is required to assure that the participation minority participants reflects the percentage representation of these populations in their geographic region and, for the AMC, the United States as a whole. As such, it is expected that the representation of participants on this trial will reflect the constitution of the respective populations.

Accrual Targets

| Ethnic Category | Sex/Gender | | | | |
|-----------------------------------------------|------------|----------|----------|----------|------------|
| | Females | | Males | | Total |
| Hispanic or Latino | 90 | + | 0 | = | 90 |
| Not Hispanic or Latino | 210 | + | 0 | = | 210 |
| Ethnic Category: Total of all subjects | 300 | + | 0 | = | 300 |
| Racial Category | | | | | |
| American Indian or Alaskan Native | 0 | + | 0 | = | 0 |
| Asian | 0 | + | 0 | = | 0 |
| Black or African American | 210 | + | 0 | = | 210 |
| Native Hawaiian or other Pacific Islander | 0 | + | 0 | = | 0 |
| White | 90 | + | 0 | = | 90 |
| Racial Category: Total of all subjects | 300 | + | 0 | = | 300 |

(A1 = A2)

(B1 = B2)

(C1 = C2)

9.4 Participant Confidentiality

All laboratory specimens, evaluation forms, reports, and other records that leave the site will be identified by coded number only to maintain participant confidentiality. All records will be kept locked. All computer entry and networking programs will be done with coded numbers only. Clinical information will not be released without written permission of the participant, except as necessary for monitoring by the IRB, the NIH, or designee.

9.5 Study Discontinuation

The study may be discontinued at any time by the IRB, the NIH, or other government agencies as part of their duties to ensure that research participants are protected.

10.0 PUBLICATION OF RESEARCH FINDINGS

Publication of the results of this trial will be governed by AMC policies. Any presentation, abstract, or manuscript will be made available for review prior to submission.

10.1 Study Participant Confidentiality

To maintain confidentiality, all laboratory specimens, evaluation forms, reports and other records will be identified by a coded number only and de-identified from the participant. Clinical information will not be released without written permission of the participant, except as necessary for monitoring by the FDA, OHRP, the AMC, or the NCI.

10.2 Study Discontinuation

This study may be discontinued at any time by the NCI, the AMC, the OHRP, or the FDA.

11.0 BIOHAZARD CONTAINMENT

As the transmission of HIV and other blood-borne pathogens can occur through contact with contaminated needles, blood, and blood products, appropriate blood and secretion precautions will be employed by all personnel in the drawing of blood and shipping and handling of all specimens for this study, as currently recommended by the Centers for Disease Control and Prevention and the National Institutes of Health.

All dangerous goods materials, including diagnostic specimens and infectious substances, must be transported according to the instructions detailed in the International Air Transport Association (IATA) Dangerous Goods Regulations.

APPENDIX I: SCHEDULE OF EVENTS

| Evaluation | Screening | Enrollment [¥] (Visit 1) (Baseline) | Post-Procedure Call (2-5 weeks after V 1, 3, 5) | Visit 2* Month 6 | Visit 3* Month 12 | Visit 4* Month 18 | Visit 5* Month 24 |
|---------------------------------------------------------------|----------------|----------------------------------------------------|-------------------------------------------------------|---------------------|----------------------|----------------------|----------------------|
| Informed consent | X | | | | | | |
| Documentation of HIV | X | | | | | | |
| Medical history, medication history, ANC, platelets | X ¹ | | | | | | |
| Medical record review, HIV viral load, CD4 count ² | | X | | | | | X |
| Pregnancy test (urine) | X | X ³ | | | X | | X |
| Baseline questionnaire | | X | | | | | |
| Post procedure questionnaire via phone call | | | X | | | | |
| Follow-up questionnaire | | | | X | X | X | X |
| Targeted physical and anogenital exam | | X | | X | X | X | X |
| Anal cytology ⁴ | | X | | X | X | X | X |
| Anal swab for HPV (1 in ThinPrep) | | X | | X | X | X | X |
| Anal swab in lysis tube for Arbor Vita | | X | | X | X | X | X |
| Cervical cytology ⁵ | | X | | | X | | X |
| Cervical swab for HPV (1 in ThinPrep) | | X | | | X | | X |
| HRA with biopsy of lesions ⁶ | | X | | | X | | X |
| Anal cytology slides ⁷ | | X | | X | X | X | X |
| Anal biopsy slides ⁷ | | X | | | X | | X |
| ACSR blood specimen (participant consent) | | X | | | | | |

* Visits 2-5 (and associated specimens) may occur within 14 days prior to the target visit date and up to 160 days after the target visit date.

[¥] All Study Evaluations for Enrollment visit must be completed within 50 days before the enrollment visit.

1. Only collect ANC and platelets if results are not available from routine clinical care within 120 days before enrollment.
2. Only collect HIV viral load and CD4 counts/percentages if results are not available from routine clinical care within 120 days before Visit 1 and Visit 5.
3. Pregnancy test will not be required at Visit 1 if the pregnancy test for Screening/eligibility review was performed less than 72 hours prior to study entry.
4. Local anal cytology specimens may be collected in liquid medium as per standard of care of study site (either ThinPrep or Surepath).
5. For the enrollment visit local cervical cytology specimens may be collected up to 42 days before the enrollment visit date.
6. Perform HRA-directed biopsies up to 6 of the most abnormal appearing areas. Each study participant will have at least two biopsies at HRAs (visits 1, 3, 5). If fewer than two directed biopsies are taken from two different quadrants, then random biopsy/biopsies will be done such that there will be at least two biopsies from at least two different quadrants. These biopsies can be from the anal canal or perianus.
7. All baseline anal cytology slides for the first 6 months after a site is activated will be submitted for an evaluation of quality control. All anal histology slides taken during Visits 1-5 will be submitted to the AMC Biorepository for central pathology review. Slides will be submitted as per [Appendix VI](#) for details.

APPENDIX II: PERFORMANCE STATUS SCALES

| Karnofsky Performance Scale | | ECOG Performance Status Scale | |
|-----------------------------|--------------------------------------------------------------------------------|-------------------------------|---------------------------------------------------------------------------------------------------------------------------------------------------------------------------------------|
| Percent | Description | Grade | Description |
| 100 | Normal, no complaints, no evidence of disease. | 0 | Normal activity. Fully active, able to carry on all pre-disease performance without restriction. |
| 90 | Able to carry on normal activity; minor signs or symptoms of disease. | | |
| 80 | Normal activity with effort; some signs or symptoms of disease. | 1 | Symptoms, but ambulatory. Restricted in physically strenuous activity, but ambulatory and able to carry out work of a light or sedentary nature (e.g., light housework, office work). |
| 70 | Cares for self, unable to carry on normal activity or to do active work. | | |
| 60 | Requires occasional assistance, but is able to care for most of his/her needs. | 2 | In bed <50% of the time. Ambulatory and capable of all self-care, but unable to carry out any work activities. Up and about more than 50% of waking hours. |
| 50 | Requires considerable assistance and frequent medical care. | | |
| 40 | Disabled, requires special care and assistance. | 3 | In bed >50% of the time. Capable of only limited self-care, confined to bed or chair more than 50% of waking hours. |
| 30 | Severely disabled, hospitalization indicated. Death not imminent. | | |
| 20 | Very sick, hospitalization indicated. Death not imminent. | 4 | 100% bedridden. Completely disabled. Cannot carry on any self-care. Totally confined to bed or chair. |
| 10 | Moribund, fatal processes progressing rapidly. | | |
| 0 | Dead. | 5 | Dead. |

APPENDIX III: ANAL SAMPLING PROCEDURES

All anal cytology specimens will be examined at the local institution.

The participant should undress from the waist down, and either bend over the exam table or lay on their side in the fetal position. The examiner should use one hand to spread the buttocks and expose the anal verge.

Procedure for obtaining an anal swab specimen

A Dacron swab moistened in tap water will then be inserted as far as is comfortable into the anus, a minimum of 1-2 inches. If there is difficulty inserting the swab, the participant should also retract their buttocks and the swab reoriented in the canal. With pressure on the distal end of the swab rotate it firmly in a circular fashion for approximately 20 seconds and slowly remove from the canal. Do not retract the buttocks when the swab is close to the verge to ensure that it is sampled as well. Immediately immerse the swab in a liquid-cytology vial agitating vigorously over 20 to 30 seconds to disperse the cells.

The order of anal specimen collection will be determined at the time of registration and will remain constant for a given participant for every study visit.

The three anal swab specimens will be collected from each study participant in the order as designated at the time of enrollment. **The sequence of collection for these three swabs will be randomly assigned by the data entry system, AdvantageEDC, at the time of enrollment.** The site should print the collection order for the specimens in the enrollment confirmation email message and save it to the study file for future reference.

Anal swab specimens for a given study participant will always be collected in the same sequence at every visit. For example, participant 1 may be assigned to have specimens collected in the order “local,” “thinprep”, and “lysis” at all visits, whereas participant 2 may be designated the order “thinprep,” “lysis,” and “local” at all visits, etc. The three swabs collected are:

- Dacron Swab “local” [Identified as “Dacron Swab (local cytology)” in the swab sequence assignment at enrollment]. This swab will be placed in the cytology medium required for local processing for anal cytology.
- Dacron Swab “thinprep” [Identified as “Dacron Swab (ThinPrep HPV)”). This swab will be placed in a 20 mL ThinPrep (PreservCyt) media vial (for research anal HPV analyses) and stored in a refrigerator (2-8° C) as soon as possible after collection.
- Puritan Medical Products Dacron Swab “lysis” [Identified as “Swab for Arbor Vita (“lysis” tube)”). This swab will be placed in a tube provided by Arbor Vita (a.k.a., “lysis” tube) immediately after collection. The swab stem will be broken to deposit the entire swab head so that the cap will fit on the tube. Instructions on isolating the swab head in the lysis tube can be found on the AMC AIDS Malignancy Consortium website at www.amcoperations.com. Anal swabs placed in the Arbor Vita-supplied tubes should be frozen immediately at -80° C. The sites may batch ship these specimens EVERY 3 months.

Note: While the anal specimen collected for Arbor Vita will be stored “dry,” the swab may be pre-moistened with tap water before the sampling procedure for patient comfort.

Sites are strongly encouraged to implement local processes to ensure that the assigned anal

cytology swab specimen collection sequence is maintained during the study. Sites should label swab collection tubes with the assigned collection sequence using a marker before sampling. The actual collection sequence must be documented in the source for each anal sampling procedure. A sample source document for this purpose is provided on the AMC AIDS Malignancy Consortium website at www.amcoperations.com.**Sites will be required to report the actual sequence of swab collection in the data entry system.**

The Puritan swab will be provided by the AMC, and the “lysis” tube for the Arbor Vita swab will be provided by Arbor Vita. The ODMC will place all orders for the Puritan swabs and collection tubes for the dry swab specimen on the site’s behalf. All requests for supplies may be placed with the AMC ODMC via email ([contact]) or [contact]). This request may be made using the attached AMC-084 Cytology Supplies Request Form. The Cytology Supplies Request Form can be found on the AMC AIDS Malignancy Consortium website at www.amcoperations.com.

Arbor Vita: Use the Puritan™ Polyester-Tipped Applicator to obtain the anal specimen and then place the swab in a 1.5ml eppendorf tube (lysis tube) and store the lysis tubes at -80°C. Site will then batch ship the lysis tubes on dry ice to the AMC Biorepository every 3 months. See the AMC-084 MOP for shipping instructions.

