| PRIMARY OBJECTIVES: | 
1) To determine the sensitivity and specificity of HPV testing using different methods of detection, including HPV Hybrid Capture 2 (HC2), HPV mRNA assays (APTIMA) and Arbor Vita OncoE6 HPV test and whether they improve the screening performance of routine anal cytology for the detection of anal HSIL when measured against the gold standard, biopsy-proven HSIL.2) To determine the prevalence and risk factors for prevalent HSIL in HIV-positive women.3) To determine incidence and risk factors associated with HSIL and anal HPV over 2 years among HIV positive women undergoing semi-annual anal evaluations. |
| EXPLORATORY OBJECTIVES: | 
1) To evaluate the acceptability of anal cancer screening among HIV-positive women.2) To collect data on quality of life and health care costs (including non-direct health care costs and time costs) for an economic evaluation of the cost-effectiveness of anal cancer screening strategies in HIV-positive women. |

PROTOCOL SCHEMA

Visit 0: Pre-Entry (Screening)

- Informed consent for study participation and ACSR donation
- Document HIV diagnosis, medical and medication history
- Urine pregnancy test
- Collect ANC and platelet count if not done for routine care \leq 120 days prior to enrollment

Visit 1: Enrollment (Baseline)

- Baseline Questionnaire at visit
- Targeted physical and anogenital exam, medical record and medication review
- Collect CD4 count/percentage and HIV viral load if results not available from routine care \leq 120 days prior
- Collect 2 cervical/vaginal specimens (1 for local cytology, then 1 in ThinPrep for central HPV testing)
- Collect 3 Anal Swabs (1 for local cytology, then 1 in ThinPrep for central HPV testing, and 1 swab placed in a lysis tube provided by ArborVita).
- HRA with minimum of 2 biopsies (up to 6 directed biopsies of areas suspicious for AIN; random biopsies if fewer than 2 directed biopsies are taken)
- Blood for ACSR donation (optional; 2 yellow top tubes if consent given; can be collected during subsequent visits)
- Post-Procedure Questionnaire via phone call within 1-5 weeks after visit
- Send cervical and anal ThinPrep specimens to AMC Biorepository within 4 weeks of collection

Visit 2 (Month 6) AND Visit 4 (Month 18) Follow Up (-14 / +160 days)

- Follow-up Questionnaire at visit
- Targeted physical and anogenital exam, medical record and medication review

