- 3 Anal Swabs (1 for local cytology, then 1 in ThinPrep for central HPV testing, and 1 swab placed in a lysis tube provided by ArborVita)
- Send anal ThinPrep specimens to AMC Biorepository within 4 weeks of collection

Visit 3 (Month 12) AND Visit 5 (Month 24) Follow Up (-14 days / +160 days)

- Follow-up Questionnaire at visit
- Targeted physical and anogenital exam, medical record and medication review
- Collect CD4 count/percentage and HIV viral load if results not available from routine care \leq 120 days prior for Visit 5 only
- Collect 2 Cervical Swabs (1 for local cytology, then 1 in ThinPrep for central HPV testing)
- Collect 3 Anal Swabs (1 for local cytology, then 1 in ThinPrep for central HPV testing, and 1 swab placed in a lysis tube provided by ArborVita)
- HRA with minimum of 2 biopsies (up to 6 directed biopsies of areas suspicious for AIN; random biopsies if fewer than 2 directed biopsies are taken)
- Post-procedure Questionnaire via Phone Call within 1-5 weeks after visit
- Send cervical and anal ThinPrep specimens to AMC Biorepository within 4 weeks of collection

Cytology and Histology Slide Submission Requirements

- **Quality Control:** Submit all baseline anal histology slides collected from the first six months after enrollment of the first study participant at a given study site. These slides should be batch shipped to the AMC Biorepository as soon as possible 6 months (no more than 9 months) after enrollment of the first study participant at each study site.
- **Central Pathology Review:** All anal histology slides from Visits 1-5 that were not submitted for quality control must be submitted for central review. All slides may be batched for submission to the AMC Biorepository every 6 months after the first subject's enrollment at that site.

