The novel methods of detection (HPV hybrid capture 2, HPV mRNA assays (APTIMA) and Arbor Vita Onco E6 HPV test) will be evaluated to determine if they improve sensitivity or specificity compared to routine anal cytology using McNemar’s test. With 30 HSIL women, a 20% increase in sensitivity with 25% of participants with discordant results can be detected at the one-sided 0.05 significance level with 78% power. With 270 women negative for HSIL, a 20% increase in specificity with 25% of participants with discordant results can be detected at the one-sided 0.05 significance level with 99% power. Positive and negative predictive values will be assessed for each method of detection.

To determine incidence of HSIL, we will use the information from the women whose initial HRA examination is negative for HSIL. If these women are followed for an average of 1.8 months, we would expect $1.8 \times 270 = 486$ person-years of follow-up. The table below shows the 95% Poisson confidence intervals for two levels of the underlying incidence of HSIL with 486 person-years of observation:

| Underlying incidence of HSIL per 100 person-years | 95% Poisson confidence interval (per 100 person-years) |
|---------------------------------------------------|--------------------------------------------------------|
| 2.06 | (1.11, 3.82) |
| 3.09 | (1.86, 5.12) |

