APPENDIX V: CERVICAL/VAGINAL SAMPLING PROCEDURES

Procedure for obtaining cervical/vaginal cytology samples

The participant should undress from the waist down, and lay on her back on the exam table. The examiner should follow standard pelvic exam procedures. Collection for two cervical* specimens will be collected. The cervical cytology specimen (using the “broom”, cytobrush, and/or spatula) will be collected first, and will be placed in the standard liquid-based cytology media at each local institution (e.g., ThinPrep or SurePath). The second specimen will be collected by “broom,” cytobrush, and/or spatula and dispersed in a 20 ml vial of ThinPrep (PreservCyte) to be used for all three HPV analyses.

See [Appendix VI](#) for local processing of the first sample for cytology.

See [Appendix VII](#) for processing and shipping of the second sample collected for HPV analyses.

***If the participant has had a hysterectomy, then the specimens should be collected from the vaginal apex instead of the cervix.**

APPENDIX VI: PROCEDURES FOR PROCESSING LOCAL CYTOLOGY/HISTOLOGY SPECIMENS AND CENTRAL PATHOLOGY REVIEW

Local cytology/pathology specimen processing

- 1) *Local cytology reading:* Run the liquid cytology sample (ThinPrep or Surepath) as is, per protocol at the local institution. The reading from the cytopathology lab will be submitted in the appropriate eCRF in AdvantageEDC. The study investigators will have access to the cytopathology reading via the AMC Operations web site (secure access).
- 2) *Residual specimens:* If the participant consented to donate residual study specimens to the ACSR for future testing, the residual liquid cytology medium after performing the local anal and cervical cytology readings will be sent to AMC Biorepository within 4 weeks of specimen collection (see [Appendix XI](#) for labeling and shipping requirements).
- 3) *Histology:* Process as per protocol at the local institution. The reading from the pathology lab will be submitted in the appropriate eCRF in AdvantageEDC. The study investigators will have access to the cytopathology reading via the AMC Operations web site (secure access).

Suggested p16 immunohistochemical (IHC) staining for local pathologists

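### Does the Schema's cytology-then-ThinPrep wording, with no planned analysis of swab order, threaten the comparison of HPV tests with anal cytology?

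*Combined protocol and SAP*

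**What the plan says.** Appendix III governs anal sampling. It states that "The sequence of collection for these three swabs will be randomly assigned by the data entry system, AdvantageEDC, at the time of enrollment". The order is then held constant for each woman at every visit. The site is to print the order from the enrollment confirmation email, file it and mark the tubes before sampling. The actual order must go into the source record, and "Sites will be required to report the actual sequence of swab collection in the data entry system". Local processes to maintain the order are strongly encouraged rather than required.

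The Protocol Schema is shorter. At Visit 1 it reads "Collect 3 Anal Swabs (1 for local cytology, then 1 in ThinPrep for central HPV testing, and 1 swab placed in a lysis tube", and the follow-up visits have the same phrase: "3 Anal Swabs (1 for local cytology, then 1 in ThinPrep for central HPV testing". Neither line refers to an assigned order. The cervical line is worded alike, "Collect 2 cervical/vaginal specimens (1 for local cytology, then 1 in ThinPrep for central HPV testing", and there Appendix V does fix the order: the cytology specimen "will be collected first, and will be placed in the standard liquid-based cytology media at each local institution".

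Section 7.2.1 compares cytology with each HPV test by McNemar's test, separately in women with and without HSIL. It has no order term and no summary of order. The review items in section 8.4 do not mention swab order either.

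**The concern.** The same Schema phrase describes a fixed order for the cervix and a randomised one for the anus. A coordinator working from the Schema alone could take cytology first in every woman. Test would then be confounded with swab position for cytology against HC2 and APTIMA, because cytology has its own swab and those two assays use the ThinPrep swab.

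If a later swab picks up fewer positives, HPV sensitivity would be understated and HPV specificity overstated relative to cytology. The specificity error favours the new tests and falls in the larger group: "With 270 women negative for HSIL, a 20% increase in specificity with 25% of participants with discordant results can be detected". Since neither 7.2.1 nor 8.4 plans to look at the reported order, such a departure could pass through the planned analysis unseen.

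**Working it through.** **Inputs from section 7.1.** One-sided α = 0.05; 25% discordant pairs; 30 women with HSIL and a 20-point gain in sensitivity (stated power 78%); 270 women without HSIL (stated power 99%).

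**Assumed inputs, not in the documents.** L = loss of positivity for whichever of the two swabs is taken later (5 or 10 points, same for both tests). f = share of women given cytology first whatever was assigned. Assigned order is taken as balanced between cytology-first and ThinPrep-first, and discordance is held at 25%.

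**Step 1, the plan's own figures.** Enumerate the number of discordant pairs m ~ Binomial(n, 0.25) and the x pairs favouring HPV, x ~ Binomial(m, q), with q = (0.25 + d)/(2 × 0.25). Reject when (2x − m)/√m ≥ 1.645. With n = 30 and d = 0.20, q = 0.90 and power is 0.776, matching 78%. With n = 270, power exceeds 0.99, matching 99%.

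**Step 2, net bias.** The cytology-first share is 0.5 + f/2 and the ThinPrep-first share is 0.5 − f/2. HPV loses L in the first group and cytology loses L in the second, so the net shift is L(0.5 + f/2) − L(0.5 − f/2) = f × L. At f = 0 it is zero whatever L is.

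**Step 3, effect on the two tests.** Sensitivity uses d = 0.20 − fL with n = 30. Specificity with no true difference uses d = fL with n = 270.

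| f | Sensitivity power, L = 5 / 10 points | False claim of better HPV specificity, L = 5 / 10 points |
|---|---|---|
| 0 | 0.776 / 0.776 | 0.050 / 0.050 |
| 25% | 0.713 / 0.648 | 0.109 / 0.205 |
| 50% | 0.648 / 0.518 | 0.205 / 0.502 |
| 100% | 0.518 / 0.289 | 0.502 / 0.957 |

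The large figures require every woman to be sampled against a mandatory instruction.

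**Step 4, what a pre-specified order analysis would add.** Compare the mean paired difference between cytology-first (n₁) and ThinPrep-first (n₂) women without HSIL, two-sided 0.05. If both tests lose L, the contrast is 2L with SE = √[(0.25 − L²)(1/n₁ + 1/n₂)]. At f = 0 and L = 0.10: SE = √(0.24 × 2/135) = 0.0596; 0.20/0.0596 = 3.35; power = Φ(3.35 − 1.96) = 0.92.

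| f | n₁ vs n₂ | Power, L = 10 points | Power, L = 5 points |
|---|---|---|---|
| 0 | 135 vs 135 | 92% | 38% |
| 25% | 169 vs 101 | 90% | 36% |
| 50% | 202 vs 68 | 83% | 30% |
| 75% | 236 vs 34 | 60% | 19% |
| 100% | 270 vs 0 | no contrast | no contrast |

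In women with HSIL (15 vs 15, L = 10 points) power is about 20%. A sensitivity of 75% in one order group has a 95% half-width of 1.96 × √(0.75 × 0.25/15) = 0.22.

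**Step 5, which text governs.** Section 4.3.7 sends the reader to Appendix III for both anal cytology and anal HPV sampling. Appendix III makes the assigned order mandatory; its encouragement wording concerns only local back-up processes. The order reaches the site with each enrollment confirmation. A site following the Schema would have to disregard all of this.

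**The case for a change.** The strongest case for acting is that the sponsor thought order important enough to randomise, hold constant and record, yet planned no use of the record. A check chosen after results are known is weaker than a pre-specified one, an audit of individual records does not measure an order effect, and the cost would be one cross-reference, one table and one secondary analysis from data already collected.

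The textual part of this stands: the Schema line is loose, and no order summary is pre-specified. Three things limit it.

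- Randomised order protects the paired comparison through the design. An order term is not needed for validity.
- The departure would not be invisible. The actual order is in the database, and Appendix VIII has audits check source documents for protocol compliance. Section 1.1.9 also has the co-chairs watch, over the first six months, whether sampling gives enough material. That is not a test of order, but it bears on poor yield, the mechanism assumed here.
- The secondary analysis is weakest where the bias would be largest. It loses its contrast as f rises, it is no longer a randomised comparison if departures cluster by site, and in women with HSIL it is only descriptive.

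**Conclusion.** No change to the plan is called for. The Schema wording is a clerical looseness in a summary, and Appendix III is explicit on the point. Under the plan as written (f = 0) sensitivity power stays at 78% and the specificity error rate at 5%, and neither bias arises. Harm needs two things together that the documents do not show: sites departing from a mandatory order, and a later swab yielding less. At 25% departure with a 5- or 10-point loss it would be material (11% or 20.5% false claims of better specificity), so adherence is worth an analyst's glance. The reported order allows that without an amendment: an assigned-versus-actual count by site is an ordinary data check. McNemar's test would remain primary either way. This conclusion assumes that the random assignment is roughly balanced between cytology-first and ThinPrep-first and that sites largely follow it.
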